THE QUANTUM TRIP TRIAL (QTT)

STATISTICAL ANALYSIS PLAN

Can a single administration of psilocybin reduce alcohol intake in patients with alcohol use disorder? A randomized, double-blinded, placebo-controlled clinical trial.

Protocol Number #PSILO4ALCO
EU CT 2024-517497-17-01
Clinicaltrials.gov: NCT05416229

SAP date/status February 17, 2026/ first edition
Protocol version: February 14, 2024/Third edition

SAP contributors:

Investigator

[name], PhD
Mental Health Center, Frederiksberg and Bispebjerg Hospital

Sponsor and Principal Investigator

[name] MD DMSc, Professor
Mental Health Center, Frederiksberg and Bispebjerg Hospital
University of Copenhagen, Denmark

Senior statistician

[name] PhD, Professor
Section of Biostatistics, University of Copenhagen, Denmark

Signatures:

[name]

_____ Date: _____

[name]

_____ Date: _____

[name]

_____ Date: _____

INTRODUCTION

The aim of the Quantum Trip Trial (QTT) was to test whether a single dose of 25 mg psilocybin with psychotherapy could reduce alcohol intake in patients diagnosed with alcohol use disorder.

This statistical analysis plan prespecifies analyses for the primary and secondary outcomes of the trial and is intended to support multiple planned publications arising from the study.

Prior to analyses, the statistical analysis plan will be uploaded to ClinicalTrials.gov and the dataset will be locked. All analyses will be conducted under blinded conditions.

HYPOTHESES

- **Primary hypothesis:**

- Participants receiving psilocybin will show a greater reduction in alcohol consumption as measured by percentage heavy drinking days the past 28 days using the Timeline Followback Method (TLFB) from baseline to Week 12 compared to participants receiving placebo.

- **Secondary hypotheses:**

- Participants receiving psilocybin will show greater increases in neuroplasticity, measured in whole-blood levels of blood brain-derived neurotrophic factor (BDNF), from baseline to Week 1 compared with participants receiving placebo.
- A mean-centering Partial Least Squares analysis will show a group (psilocybin vs placebo) × condition (alcohol vs neutral) interaction, in the anterior cingulate cortex, insula, striatum, and frontal gyrus where the neural differentiation between alcohol and neutral cues will differ between psilocybin and placebo groups, with reduced differentiation in the psilocybin group. Additionally, in-scan craving ratings following viewing pictures of alcohol (VAS 0-100) will be lower in participants randomized to psilocybin relative to placebo.
- At Week 1, resting-state functional connectivity, defined as Fisher r to z -transformed correlations between BOLD time series extracted from the striatum (defined using the Tian subcortical atlas) and pre-specified regions of the salience network (defined using the Schaefer/Yeo cortical atlas), will differ between participants randomized to psilocybin and placebo.

- **Exploratory hypotheses:**

- Lower Week-1 neural differentiation between alcohol and neutral cues (lower latent variable scores from a separate single-group Partial Least Squares analysis collapsing across treatment groups) will be associated with greater reductions in alcohol consumption from baseline to Week 12. Differences between psilocybin and placebo

groups in striatal functional connectivity (striatum-salience network and striatum-prefrontal) at Week 1 will be associated with changes in alcohol consumption from baseline to Week 12.

- Resting-state functional connectivity in the Control networks (defined using the Schaefer/Yeo cortical atlas) will be lower in the psilocybin group compared to the placebo group at Week 1 and will be associated with changes in alcohol consumption from baseline to Week 12.
- Greater acute subjective effects measured on the dosing day will be associated with greater reductions in alcohol consumption from baseline to Week 12.
- At Week 1, resting-state functional connectivity, defined as Fisher r to z -transformed correlations between BOLD time series extracted from the striatum (defined using the Tian subcortical atlas) and all brain regions (defined using the Schaefer/Yeo cortical atlas), will differ between participants randomized to psilocybin and placebo. Results will be presented as effect sizes i.e., Cohen's D , and inferential statistics i.e., p -values will not be reported.
- Task-based fMRI analyses will be repeated using a GLM in SPM to provide a map of task response as well as group-level effects on the task response.

STUDY METHODS

STUDY DESIGN

The QTT trial was a randomized, double-blinded, placebo-controlled, parallel-group, single-site clinical trial for 12 weeks (main trial) and a long-term follow-up 26 weeks after the intervention. The trial compared single-dose psilocybin therapy vs placebo therapy. The treatment involved two preparation sessions, a high-dose psilocybin session (25 mg) or placebo (inert substance) session, and three integration sessions. Baseline data was collected at screening visit and outcomes were assessed 1, 4, 8, 12 (primary endpoint) and 26 weeks after the psilocybin/placebo session. A sub-group of participants underwent fMRI scan 1 week after the intervention (no baseline scan).

RANDOMIZATION

The participants were randomized in two groups (1:1): psilocybin therapy or placebo therapy. The randomization was stratified in terms of age (20-45, 46-70 years), sex, and baseline alcohol consumption i.e. the number of heavy drinking days in the last 28 days before inclusion measured by the TLFB-method (5-15, 16-28 days). The randomization tool in REDCap was used. Patients, investigators, other caregivers performing assessments, and persons performing data analysis have been blinded from the time of randomization and until the time of database unlock.

SAMPLE SIZE

The study was initially designed to enroll 90 participants, based on an a priori power analysis informed by effect sizes reported in the open-label pilot study by Bogenschutz and colleagues (2015). Assuming a two-

sided alpha level of 0.05 and 90% power, the required sample size was estimated to be 27 participants per treatment arm. Anticipating a dropout rate of approximately 40%, the total planned enrollment was therefore set at 90 participants. Due to delays associated with the COVID-19 pandemic and lack of financial resources to continue the study, recruitment was terminated before reaching the intended enrollment target. Following the decision to stop recruitment, a revised power calculation—based on the originally specified primary endpoint and the same effect size assumptions as the initial power analysis—indicated that 22 participants per treatment arm would provide approximately 85% power, corresponding to a total of 44 completers. As of December 2025, the observed dropout rate was substantially lower than anticipated (13%), resulting in 59 enrolled participants, of whom 51 completed the primary endpoint assessment. The number of completers therefore exceeded the minimum sample size required according to the revised power calculation. Of these, 28 completed fMRI scans, however only those with complete behavioural data and adequate quality imaging data for analyses will be retained for analyses. Imaging data will be quality controlled using fMRIPrep.

TRIAL POPULATION

Recruitment

Recruitment began September 2023 and ended September 2025. Last patient's last visit in the main trial i.e., the 12-week outcome assessment was on 22nd December 2025. Last patient's last visit concluding the entire study i.e., the 26-week follow-up will be end of March 2026. Participants were recruited in part from outpatient clinics, but predominantly from society via advertisement.

Eligibility

Treatment seeking individuals aged 20-70, weighing 60-95kg, diagnosed with AUD and alcohol dependence according to DSM-V and ICD-10, respectively, who had at least 5 heavy drinking days within the past 28 days of screening, and no co-occurring substance use disorders (except nicotine) and no concomitant pharmacotherapy for AUD.

OUTCOMES

OUTCOME CATEGORY	SOURCE	TIME POINTS	PRIMARY COMPARISON (BETWEEN-GROUP DIFFERENCE)
Primary			
1. Percentage of Heavy Drinking Days (PHDD)	TLFB/28 days	BL, W4, W8, W12	W12, adjusted for BL
Secondary			
2. Alcohol consumption:			
• % drinking days	TLFB/28 days	BL, W4, W8, W12	W12, adjusted for BL
• Drinks per day	TLFB/28 days	BL, W4, W8, W12	W12, adjusted for BL
• Drinks per drinking day	TLFB/28 days	BL, W4, W8, W12	W12, adjusted for BL
• Total alcohol (g/day)	TLFB/28 days	BL, W4, W8, W12	W12, adjusted for BL
• % abstinent days	TLFB/28 days	BL, W4, W8, W12	W12, adjusted for BL

•	WHO risk levels	TLFB/28 days	BL, W4, W8, W12	W12, adjusted for BL
•	PEth	Blood	BL, W4, W8, W12	W12, adjusted for BL
•	GGT	Blood	BL, W12	W12, adjusted for BL
•	ALAT	Blood	BL, W12	W12, adjusted for BL
•	MCV	Blood	BL, W12	W12, adjusted for BL
3.	Brain imaging and neuroplasticity			
•	Alcohol cue-related BOLD response and in-scan craving ratings (alcohol > neutral)	fMRI	W1	W1 (post-treatment only)
•	Resting-state functional connectivity between striatum and salience -network regions	fMRI	W1	W1 (post-treatment only)
•	BDNF	Blood	BL, dosing, W1, W12	W1, adjusted for BL
4.	Psychometrics			
•	SETS	Questionnaire	BL	BL
•	PACS	Questionnaire	BL, W1, W4, W8, W12	W12, adjusted for BL
•	AUDIT	Questionnaire	BL, W12	W12, adjusted for BL
•	DUDIT	Questionnaire	BL, W12	W12, adjusted for BL
•	AASE	Questionnaire	BL, W1, W4, W8, W12	W12, adjusted for BL
•	MDI	Questionnaire	BL, W1, W4, W8, W12	W12, adjusted for BL
•	MAAS	Questionnaire	BL, W1, W4, W8, W12	W12, adjusted for BL
•	AAQ	Questionnaire	BL, W1, W4, W8, W12	W12, adjusted for BL
•	SF-36	Questionnaire	BL, W4, W12	W12, adjusted for BL
•	NEO-PI	Questionnaire	BL, W4, W12	W12, adjusted for BL
•	FTND	Questionnaire	BL, W4, W8, W12	W12, adjusted for BL
•	PEQ	Questionnaire	W4, W12	W12
5.	Acute effects			
•	SDI	VAS (0-10)	Dosing (0–360 min)	Association with W12 alcohol outcomes, adjusted for baseline
•	MEQ30 / 11D-ASC / EBI / EDI / AWE	Questionnaire	End of dosing day	Association with W12 alcohol outcomes, adjusted for baseline
6.	Safety			
•	Adverse events	AE reporting	Throughout study	Descriptive

Abbreviations: BL = baseline; W1, W4, W8, W12 = Week 1, Week 4, Week 8, and Week 12; PHDD = percentage of heavy drinking days; TLFB = Timeline Followback; WHO = World Health Organization; PEth = phosphatidylethanol; GGT = gamma-glutamyl transferase; ALAT = alanine aminotransferase; MCV = mean corpuscular volume; fMRI = functional magnetic resonance imaging; BOLD = blood oxygenation level-dependent; ROI = region of interest; BDNF = brain-derived neurotrophic factor; SETS = Stanford Expectancy Treatment Scale; PACS = Penn Alcohol Craving Scale; AUDIT = Alcohol Use Disorders Identification Test; DUDIT = Drug Use Disorders Identification Test; AASE = Alcohol Abstinence Self-Efficacy Scale; MDI = Major Depression Inventory; MAAS = Mindful Attention Awareness Scale; AAQ = Acceptance and Action Questionnaire; SF-36 = 36-Item Short Form Health Survey; NEO-PI = NEO Personality Inventory; FTND = Fagerström Test for Nicotine Dependence; PEQ = Persisting Effects Questionnaire; SDI = Subjective Drug Intensity; VAS = visual analogue scale; MEQ30 = Mystical Experience Questionnaire (30-item version); 11D-ASC = 11-Dimensional Altered States of Consciousness Rating Scale; EBI = Emotional Breakthrough Inventory; EDI = Ego Dissolution Inventory; AWE = Awe Experience Scale; AE = adverse event.

Blinding

Analyses will be carried out with the treatment groups still blinded and labeled as “group 1” and “group 2”. Before dividing participants, the statistical analysis plan will be completed, signed, and uploaded at [clinicaltrials.gov](#), and the data set locked. The final unblinding of treatment groups (psilocybin or placebo), will not be carried out until all statistical analyses are performed. The last long-term follow up-visit (Week 26) is in April 2026, and this data will be analyzed unblinded.

ANALYSIS

Population

Analyses will follow the intention-to-treat principle i.e., analyzing participants who have been randomized and who have also received a dosing with psilocybin/placebo.

Descriptive statistics

All outcomes will be presented using descriptive statistics, normally distributed data by the mean and standard deviation (SD) and skewed distributions by the median and interquartile range (IQR). Binary and categorical variables will be presented using counts and percentage.

Efficacy analyses

For continuous outcomes, analyses will use a baseline-adjusted linear mixed model for repeated measures including all observed timepoints for the given outcome. The primary estimand is the between-group difference in mean change from baseline at Week 12 (unless otherwise specified). Model assumptions will be assessed using standard diagnostic methods. If substantial deviations from model assumptions are observed, appropriate transformations of the outcome or alternative modeling approaches will be considered as sensitivity analyses.

Categorical outcomes assessed at a single time point will be analyzed using chi-square or Fisher’s exact tests as appropriate. Repeated categorical outcomes will be analyzed using GEE or generalized linear mixed models.

Missing data

Missing data will be handled using full information maximum likelihood (FIML), which uses all available observed data to estimate model parameters under the missing at random (MAR) assumption. While the

MAR assumption may not be valid we will also consider sensitivity analyses by setting missing observations to extreme but realistic values to bound realistic effect size. See below.

Sensitivity analysis

Because the MAR assumption cannot be formally tested, pre-planned sensitivity analyses will be conducted under missing not at random (MNAR) assumptions. Specifically, missingness is assumed to potentially depend on factors related the unobserved Week 12 outcome values. The following conservative scenarios will be evaluated:

- Complete-case analysis: Analyses will be restricted to participants with observed values at both baseline and the Week 12 endpoint. In the case of neuroimaging data, only complete cases will be analysed.
- Single imputation (conservative MNAR scenario): For participants with missing Week 12 data, the continuous Week 12 outcome will be imputed as a 50% reduction from the individual's baseline value (i.e., Week 12 = $0.5 \times$ baseline), and the primary analysis model will be re-estimated.

Per protocol analysis

A per-protocol (PP) analysis will be conducted including only participants who did not violate key protocol requirements through Week 12. The PP analysis is intended to estimate the effect of the intervention under full protocol adherence and will be interpreted cautiously due to the potential for selection bias.

Pre-specified mechanistic/exploratory analyses

Analyses will examine associations between selected secondary endpoints and the primary endpoint. These analyses are intended to assess relationships between outcomes and to inform hypotheses regarding potential mechanisms of action. Associations will be evaluated using correlation analyses and/or regression models as appropriate, without adjustment for multiplicity.

- Week 1 neural differentiation between alcohol and neutral cues, quantified using latent variable scores from a mean-centering Partial Least Squares (PLS) analysis of whole-brain blood oxygenation level-dependent (BOLD) responses, and associations with subsequent changes in alcohol consumption and brain-derived neurotrophic factor (BDNF) levels. Resting-state functional connectivity at Week 1 (striatum to salience-network, and within control-network connectivity) and their associations with changes in alcohol consumption and changes in BDNF levels.
- Acute subjective effects during the dosing session and their associations with changes in alcohol consumption and changes in BDNF levels.

Significance level

The primary endpoint will be tested using a one-sided significance level of 0.05 with corresponding 95% confidence intervals, reflecting an a priori directional hypothesis that psilocybin will reduce heavy drinking days compared with placebo. The direction of the primary hypothesis and the use of one-sided testing were prespecified prior to database lock and unblinding and were informed by consistent evidence from prior

clinical studies. Effects in the opposite direction, if observed, will be fully reported and interpreted descriptively. All secondary and exploratory analyses will be conducted using two-sided significance tests. For Partial Least Squares fMRI analyses, latent variable significance will be assessed via permutation testing (1,000 permutations, $p < 0.05$), with voxel reliability determined by bootstrap ratios $\geq |2.5|$ (200 bootstrap iterations). The PLS analysis will include group (psilocybin vs placebo) as a between-subjects factor, testing for group \times condition (alcohol vs neutral) interactions in whole-brain BOLD responses. Additionally, a separate single-group PLS analysis (collapsing across psilocybin and placebo groups) will be performed to derive individual latent variable scores reflecting each participant's neural differentiation between alcohol and neutral cues. These individual LV scores will be correlated with changes in alcohol consumption from baseline to Week 12. No multiplicity adjustments will be performed, and no additional covariate adjustments will be applied except for the baseline value of the endpoint in question.

Statistical software

All statistical analysis will be performed with R. fMRI data will be preprocessed using fMRIPrep v25.1.0 (<https://fmriprep.org/en/stable/>) and denoised using Nilearn in Python. Partial Least Squares analyses are performed using the Rotman-Baycrest PLS Toolbox in MATLAB. Resting-state functional connectivity analyses will be performed using custom code in MATLAB.

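### The exploratory association analyses have no treatment term, so if psilocybin works the pooled associations partly restate the arm difference and cannot inform mechanism

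*SAP*

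**What the plan says.** Three kinds of score are to be related to change in alcohol consumption.

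- **Acute subjective effects.** The exploratory hypothesis reads "Greater acute subjective effects measured on the dosing day will be associated with greater reductions in alcohol consumption from baseline to Week 12". The mechanistic/exploratory section repeats it and adds BDNF: "Acute subjective effects during the dosing session and their associations with changes in alcohol consumption and changes in BDNF levels". The outcomes table gives the analysis for SDI and the dosing-day questionnaires as "Association with W12 alcohol outcomes, adjusted for baseline". None of these entries names an arm or a treatment term.
- **Neural cue differentiation.** Under Significance level, "a separate single-group PLS analysis (collapsing across psilocybin and placebo groups) will be performed to derive individual latent variable scores", and then "These individual LV scores will be correlated with changes in alcohol consumption from baseline to Week 12". Pooling is explicit here.
- **Week 1 connectivity.** The striatal hypothesis takes the contrast between the two arms as its subject: "groups in striatal functional connectivity (striatum-salience network and striatum-prefrontal) at Week 1 will be associated with changes in alcohol consumption from baseline to Week 12". Control-network connectivity "will be lower in the psilocybin group compared to the placebo group at Week 1 and will be associated with changes in alcohol consumption". Neither says how treatment enters the association.

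The Significance level section then sets a general rule: "no additional covariate adjustments will be applied except for the baseline value of the endpoint in question". The mechanistic section allows correlation or regression as appropriate and gives the purpose as informing hypotheses about how the treatment acts.

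**The concern.** The plan itself expects treatment to change drinking (primary hypothesis), BDNF, cue differentiation and connectivity (secondary and exploratory hypotheses). Acute effects are compared between 25 mg psilocybin and an inert substance, so a wide separation between arms is plausible. Treatment is then a common cause of the score and the outcome. If both arms are analysed together without it, any score that separates the arms will correlate with drinking change, even when participants within an arm who score higher do no better.

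At stake is the reading of the mechanistic results. A pooled correlation cannot distinguish a stronger experience leading to less drinking from psilocybin producing both. The artefact arises when the drug works, which is the case in which these results would attract most attention. The SAP is meant to support several publications.

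**Working it through.** **1. Drinking effect implied by the plan.** The Sample size section gives 27 per arm, 90% power and two-sided alpha 0.05. By the normal approximation for two means:

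d = (1.960 + 1.282) × √(2/27) = 0.882.

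Check against the revised figure of 22 per arm and about 85% power: 0.882 × √(22/2) − 1.960 = 0.966, and Φ(0.966) = 0.833. If 27 was rounded up from just over 26, d is up to 0.899 and power up to 0.847. The stated 85% is therefore reproduced to within about 2 points. Enrolment also agrees: 54/0.60 = 90.

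**2. Correlation induced by treatment alone.** With 1:1 allocation, no association within arms, and arm separations D in the score and d in the outcome (in within-arm SDs):

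r = [D/√(D² + 4)] × [d/√(d² + 4)].

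Adjusting for the endpoint's baseline does not remove this, because randomisation makes baseline independent of arm in expectation.

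For d = 0.882 the second factor is 0.882/√4.778 = 0.404.

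- Acute scores, D = 2: 0.707 × 0.404 = 0.285. D = 3: 0.832 × 0.404 = 0.336. In simulation the mean r is 0.29 and 0.34.
- Imaging scores, D = 0.5, 0.8 and 1.0: r = 0.10, 0.15 and 0.18.

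For scale, two-sided significance at 0.05 needs |r| above 2.010/√(49 + 2.010²) = 0.276 at n = 51, and above 2.056/√(26 + 2.056²) = 0.374 at n = 28.

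**3. How often the pooled test is significant.** Simulation used normal scores, near-equal arms, no within-arm association and a two-sided 0.05 test. The samples are the 51 completers and the 28 scanned participants (before imaging quality control) given under Sample size. All values of D are assumptions, as is every d other than 0.88.

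| Analysis | D (SD) | d | Pooled, no treatment term | With treatment |
|---|---|---|---|---|
| Acute, n = 51 | 2 | 0.88 | about 55% | about 5% |
| Acute, n = 51 | 3 | 0.88 | about 71% | about 5% |
| Acute, n = 51 | 2 | 0.5 | about 23% | about 5% |
| Acute, n = 51 | 3 | 0.5 | about 30% | about 5% |
| Acute, n = 51 | 2 or 3 | 0 | about 5% | about 5% |
| Imaging, n = 28 | 0.5 | 0.88 | about 8% | about 5% |
| Imaging, n = 28 | 0.8 | 0.88 | about 12% | about 5% |
| Imaging, n = 28 | 1.0 | 0.88 | about 15% | about 5% |

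**The case against.** **The covariate rule cannot be a literal ban on treatment.** The efficacy models must contain treatment, so the rule more naturally targets covariates such as age or sex. A within-arm analysis is a choice of population and would not breach it. This stands in part: a reader might infer that the SAP forbids any arm-specific analysis, and it does not. But in an association model the score is the term under test and treatment would be an additional covariate. For acute effects the outcomes table lists baseline as the only adjustment, and no within-arm analysis is planned. The freedom to use regression as appropriate does not supply the missing term.

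**Pooling is stated only for the PLS scores.** This stands. For acute effects and connectivity it is inferred from the absence of any restriction together with the covariate rule. The striatal wording about group differences suggests that group may be meant to enter, without saying how.

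**Collapsing the arms in the PLS is defensible.** This stands. It puts all participants on one axis that is not tuned to separate the arms. The difficulty lies in the later correlation.

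**The size depends on assumptions.** This stands. The separations are not in the documents, and the d of 0.88 derives from effect sizes in an open-label pilot. A reader might also apply a 3 SD separation to the 28 scanned participants and obtain about 45%. That matches no main planned analysis, because acute scores are not limited to scanned participants and nothing suggests that imaging scores separate so widely.

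**The analyses are exploratory and claim no causal mediation.** True, and this limits severity. The fault, however, is in what is estimated, which the label exploratory does not cure. A within-arm slope would not prove mechanism either, since participant characteristics could still confound it, but it would no longer contain the arm difference.

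**Conclusion.** The point holds, with moderate severity. As written, the exploratory associations of acute effects, PLS scores and Week 1 connectivity with change in drinking or BDNF carry no treatment term, and the pooled results would partly restate any treatment effect.

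The distortion is potentially large for acute effects and modest for imaging scores, under the assumed separations. It is conditional: a reader might infer that a spurious mechanism is bound to appear, but treatment must affect both the score and the outcome for that to happen. With no effect on drinking, the pooled test for drinking keeps its nominal 5% rate.

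Nor do the documents support reading this as a threat to the trial's main results. No primary or secondary between-group comparison changes.

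**What to change.** Exempt the exploratory association analyses from the rule that only the endpoint's baseline may be a covariate. Regress the Week 12 outcome (or the follow-up BDNF value, where BDNF is the outcome) on its baseline, treatment group and the score. The single-group PLS may stay as the way to derive scores, with the treatment term added at the association step.

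For acute effects, also report the slope within each group. The Blinding section keeps the labels group 1 and group 2 until all analyses are done, so specify the slope for both labels, and state now that the psilocybin-group slope becomes the main acute-effect result once unblinded. The adjusted models themselves need only the blinded labels.

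The cost is SAP wording, settled before analysis starts, and one model term, plus the group-specific slopes for acute effects. Confidence intervals will be wider: with near-equal arms, a within-arm slope rests on about 25 participants (51/2). Imaging has about 14 scanned participants per arm (28/2) before quality control.

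### The group-code blind promised for all analyses through Week 12 is not secured: outcomes likely to reveal the code are neither held back nor placed last

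*SAP*

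**What the plan says.** The INTRODUCTION makes a general promise: "All analyses will be conducted under blinded conditions". The Blinding section gives the form: "Analyses will be carried out with the treatment groups still blinded and labeled as" group 1 and group 2. It also gives the end point: "The final unblinding of treatment groups (psilocybin or placebo), will not be carried out until all statistical analyses are performed". The one exception is the Week 26 follow-up, of which the SAP says "this data will be analyzed unblinded". The masked set is therefore everything through Week 12. The same section requires the SAP to be signed and posted, and the data locked, before participants are divided into the coded groups.

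Other sections bear on whether the masking can last:

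- STUDY DESIGN compares 25 mg psilocybin with an inert placebo.
- The OUTCOMES table lists Subjective Drug Intensity (SDI) over 0–360 minutes of dosing, and five questionnaires (MEQ30, 11D-ASC, EBI, EDI, AWE) timed at "End of dosing day". The planned use of all six is an association with Week 12 alcohol outcomes.
- PEQ is listed with a Week 12 entry in the column for between-group comparisons. Adverse events are marked as descriptive.
- Descriptive statistics states: "All outcomes will be presented using descriptive statistics".
- RANDOMIZATION describes the end of analyst blinding differently, as the time the database is unlocked.

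**The concern.** This point concerns the data analyst's blind only, not that of patients or assessors. Two arbitrary codes mask treatment only while nothing summarised by code separates an active psychedelic from an inert substance. The outcome list contains several measures intended to register drug effects. Once one of them is seen by code, the analyst can very probably name the groups, although the formal unblinding has not taken place.

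This matters because the SAP leaves some decisions open after lock:

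- **Per-protocol set:** defined as "including only participants who did not violate key protocol requirements through Week 12", with the key requirements not listed in the SAP.
- **Imaging:** 28 participants were scanned, and scans are kept or dropped on quality and completeness.
- **Model departures:** if assumptions fail, "appropriate transformations of the outcome or alternative modeling approaches will be considered as sensitivity analyses", with no criterion for which.
- **WHO risk levels:** a repeated categorical outcome, to be analysed by GEE or a generalised linear mixed model.
- **Exploratory associations:** correlation, regression or both.

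If these are settled by someone who can tell which direction favours psilocybin, the masking no longer gives the protection for which it was adopted.

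**Working it through.** The plan gives no figure on this point, so there is none to reproduce. The check has three parts.

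**1. Is there any separation or order?** The Blinding section speaks of one locked data set and one moment of unblinding after all analyses. No section withholds the acute scales, PEQ or adverse events, assigns them to a separate analyst, or requires the primary analysis to be completed first. PEQ gives the most direct route to a summary by code, because a Week 12 group comparison is listed. Adverse events and the acute scales come in through the sentence on descriptive statistics, which covers all outcomes but does not say that they are shown by group.

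**2. How easily would one scale reveal the code?** Suppose the code with the higher mean on one acute scale is taken to be psilocybin. With n per arm, a common SD and a true standardised difference d, the difference in means in SD units has standard error √(2/n). The probability that the guess is right is therefore

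P = Φ(d / √(2/n)) = Φ(d·√(n/2)).

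Inputs:

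- **n:** SAMPLE SIZE gives 59 enrolled, 51 with the primary endpoint and 28 scanned. Even splits give 29.5, 25.5 and 14 per arm; 29, 25 and 14 are used. The numbers by arm, and the number randomised and dosed, are not given.
- **d:** not in the SAP. It is an assumption, shown over a range.

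Example for n = 25, d = 0.5: √(25/2) = 3.536; 0.5 × 3.536 = 1.768; Φ(1.768) = 0.961.

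| Assumed d | n = 14 | n = 25 | n = 29 |
|---|---|---|---|
| 0.3 | 0.786 | 0.856 | 0.873 |
| 0.5 | 0.907 | 0.961 | 0.972 |
| 0.8 | 0.983 | 0.998 | 0.999 |
| 1.0 | 0.996 | 0.9998 | 0.9999 |

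A modest acute effect is enough. The code stays hidden only if the difference between arms is close to nil.

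**3. Can the primary test be run under the codes?** Significance level makes the primary test one-sided in favour of psilocybin. Let T be the test statistic for group 1 minus group 2 on percentage of heavy drinking days, with null distribution F. If group 1 is psilocybin, the p-value is F(T); if group 2 is, it is 1 − F(T). The two sum to 1. An analyst who holds only the codes can compute both but cannot say which applies. The SAP does not say that both will be computed, so either that step is missing or the direction has to be known before the analysis is finished.

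**The case against.** The strongest case on the other side has four parts.

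**The acute scales may never be seen by code.** Their planned analysis is an association with drinking outcomes, and the SAP allows no covariate beyond baseline, so it needs no group label. This stands. It leaves PEQ as the listed comparison by group, with adverse events and the acute scales depending on how the descriptive tables are laid out.

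**A reader might infer that the code breaks at the first table, or that everything is run as one batch from one file.** The document supports neither. It gives no table order, a baseline table would reveal nothing, and the plan is meant to serve several publications. One analyst file holding both the acute scales and the primary endpoint is a fair inference from the reference to a locked data set, but it is not stated.

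**The main safeguard is prespecification, not the codes.** The SAP is signed and posted and the data locked before participants are divided. The primary outcome, week, model family, missing-data method and sole covariate are named. Transformations and alternative models are confined to sensitivity analyses, the per-protocol result is to be read cautiously, and scan quality control uses a named tool. The protocol, which was not available here, may list the key requirements. All this stands and limits the exposure.

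**The calculation measures guessing, not bias.** That is correct. It says nothing about how far any estimate would move.

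What remains is that the SAP claims a blind covering all analyses through Week 12 and contains no step that would keep it.

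**Conclusion.** The concern holds in a limited form. The SAP asserts blinding by two codes for every analysis through Week 12, but any summary by code of PEQ, adverse events or the dosing-day scales would very probably reveal psilocybin, and nothing in the plan prevents or delays such a summary. For a single acute scale with 25 per arm, the probability is 0.86 to above 0.999 for assumed standardised differences from 0.3 to 1.0. This rests on an even split, a common SD and a difference that the SAP does not give.

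It would be tempting to conclude that the primary result is compromised, or that the trial report will misstate its blinding. The documents support neither. The main features of the primary analysis are fixed before division, and the coded procedure can be followed to the letter. The exposure is mainly in the per-protocol set, the exclusions among at most 28 scans, the sensitivity models, the method for WHO risk levels and the exploratory associations.

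Two related gaps need attention in the same text: how a one-sided test is run under masked codes, and the two different descriptions of when analyst blinding ends. The change should be made, and it is most useful before participants are divided.

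**What to change.** Revise the Blinding section as follows.

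1. **Before participants are divided:** sign the per-protocol list, the imaging exclusions and the rules for choosing models and transformations, including GEE or mixed model for WHO risk levels and the method for the exploratory associations.
2. **Stage 1:** use a file without SDI, MEQ30, 11D-ASC, EBI, EDI, AWE, PEQ and adverse events. On it, run and archive, with dated code and output, the primary analysis and the other Week 12, BDNF and imaging comparisons. Compute the one-sided primary test in both directions and select the relevant p-value at unblinding.
3. **Stage 2:** only then merge the acute-effect, PEQ and adverse-event data, and run the descriptive tables and the associations that use them.
4. **Wording:** limit the blinding statements in the INTRODUCTION and the Blinding section to stage 1, and reconcile them with the statement in RANDOMIZATION that analysts are blinded until the database is unlocked.

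The cost is SAP wording and one extra data cut. Safety and acute-effect tables come later, and the blinding claim becomes narrower.
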